2.1.3.2 Vital signs

The following vital signs measurement will be collected and recorded in the eCRF: systolic blood pressure (mmHg), diastolic blood pressure (mmHg), heart rate (beat/min) and body temperature (°C).

They will be collected at baseline, 24 ± 12 hours post treatment and 7 ± 2 days post treatment.

2.1.3.3 Laboratory test

Blood routine: red blood cells count (*10¹²/L), white blood cells count (*10⁹/L), neutrophils count (*10⁹/L), lymphocytes count (*10⁹/L), monocytes count (*10⁹/L), platelets count (*10⁹/L), and hemoglobin (g/dl);

Blood biochemistry: serum creatinine (umol/L), blood urea or blood urea nitrogen (mg/dl), and serum glucose (mmol/L);

Coagulation function: Prothrombin time (sec), activated partial thromboplastin time (sec), and international normalized ratio.

The laboratory test assessment will be collected at baseline and 24 ± 12 hours post treatment.

2.2 Statistical Analysis Population

The analysis populations include intention-to-treat (ITT) population and per-protocol analysis set (PPS) for this study.

2.2.1 Intention-to-treat Population

The ITT population will include all randomized subjects according to ITT principles, regardless of their eligibility and any protocol deviations, in which subjects will be analyzed according to the group assigned by randomization. ITT is the primary efficacy analysis set for this study and will also be used for analyses of demographics, baseline characteristics, medical history and concomitant medication information.

2.2.2 Per-protocol Analysis Set

The PPS is a subset of ITT population, including all randomized subjects who have been treated in the study without major protocol deviations that may significantly impact the interpretation of efficacy results. Detailed protocol deviation criteria will be determined at the latest before database lock. Subjects entering PPS need to satisfy all the following basic criteria:

- (1) Meet all the eligibility criteria specified in the study protocol;
- (2) The subjects were randomized and received the assigned treatment.
- (3) Have a blind assessment of the 90-day outcome.

2.3 Statistical Methods

For continuous data, the following statistics will be provided: number, mean, standard deviation (SD), median, lower quartile (Q1), upper quartile (Q3), minimum and maximum, unless otherwise stated. Categorical data will be summarized in terms of the number of patients and percentages.

For summary statistics, mean, standard deviation, median and quartiles will be reported to one more decimal place than the original data, while the 95% confidence interval (CI) will be reported to 2 more decimal places. Minimum and maximum values will be reported to the same number of significant digits as the original data. In the frequency table, the percentages will keep one decimal and the p values will keep 4 decimal or will be displayed as "<0.0001".

2.3.1 Subject disposition

The total number of screened subjects and the number and proportion of subjects by treatment groups who were randomized, received study treatment, completed the study, and stopped the study early, will be provided. The number and proportion of subjects according to reasons for withdrawal from the trial were summarized descriptively, and also summarized for each analysis population by treatment groups. Where necessary, the CONSORT flow chart will be presented to describe the study subject disposition in the statistical analysis report.

2.3.2 Demography and baseline characteristics

Demographic data and other baseline characteristics will be summarized by treatment groups for this study, as follows:

- Age (years);
- Sex (female vs. male);
- Race (The Han Nationality, and Other);
- Weight (kg);
- Height (cm);
- Body mass index (BMI, kg/m^2) = weight (kg)/height (m)²

In addition, smoking and drinking history, baseline mRS, baseline GCS, baseline NIHSS scale and other information will also be summarized by treatment groups. Data listings will be provided where necessary.

2.3.3 Medical history

The medical history includes medical history of stroke, carotid artery disease, cardiac disorders, hypertension, diabetes mellitus, hypercholesterolaemia and allergy history et al.

Medical history will be summarized by treatment groups.

2.3.4 Concomitant medication

Concomitant medication including thrombolytics, anticoagulants, antiplatelets, blood pressure/lipid and blood glucose control medications and other medications taken by the subjects during the study.

Concomitant medication will be summarized by treatment groups.

2.3.5 Analysis of efficacy outcomes

All efficacy data analyses will be conducted based on ITT population; for primary and secondary outcome analysis, PPS will also be used as a supportive role.

2.3.5.1 Primary efficacy outcome

The distribution of the mRS score at day 90 will be reported for each treatment group. The primary efficacy outcome analysis will be conducted by using ordinal logistic regression analysis adjusted for prognostic factors, including center as a random effect, preferred initial thrombectomy strategy (stent retriever vs. aspiration vs. stent retriever + aspiration), onset to randomization time (continuous), mRS before stroke (categorical), age (above vs. below median), and baseline NIHSS (above vs. below median) as fixed covariates. Adjusted and unadjusted common proportional odds ratio (cOR) for 1-point improvement in the mRS score will be derived from this model as treatment effect size (intervention group vs. control group) with their corresponding 95% confidence interval (CI). In case of deviations in proportional odds assumption, the mRS score at day 90 will be compared between groups by using the Mann-Whitney U test, and Wilcoxon-Mann-Whitney generalized OR will be calculated as effect size ^[2].

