7.2 Methods for Statistical Analysis

Analyses will be performed based on the intention-to-treat (ITT) principle. Baseline data by treatment allocation will be reported with statistical procedures. Missing values for baseline

characteristics will be reported. Missing baseline characteristics will be imputed using regression imputation as appropriate. The primary outcome will be analyzed by means of an ordinal logistic regression. Pre-defined subgroups will be analyzed by testing for interaction between the specific baseline characteristic and treatment. Any reported SAE or discontinuation of assigned treatment due to an SAE will be classified using MedDRA.

Statistical analyses will be detailed in the pre-specified Statistical Analysis Plan (SAP).

The study consists of 2 interim analyses to be performed when 30% and 60% of the 90-day follow- up data have been collected. The independent data and safety monitoring board (DSMB) will adopt the Haybittle-Peto rule, and $\alpha < 0.001$ in the interim analysis will be considered as statistically significant. Because only 2 interim analyses will be performed, the conventional significance level ($\alpha = 0.0482$) will be used for final analysis. The DSMB will monitor SAEs (e.g. death, spontaneous intracerebral hemorrhage [sICH], and neurological deterioration) periodically, and the occurrence of excessive SAEs will trigger discussion regarding termination of the study.

8 Study Monitoring

Qualified Clinical Research Associates (CRAs) will be responsible for regular monitoring of this study according to the monitoring plan. The monitoring is to ensure that all parties involved in the clinical study comply with the requirements in the Good Clinical Practice (ICH-GCP/GCP) and other applicable regulations during the implementation of the study, to protect the rights of the subjects and ensure the compliance with the clinical study protocol/procedures, as well as the authenticity, completeness and accuracy of the collected data.

Monitoring procedures include one or more visits before study initiation, regular monitoring visits during the study according to the agreed frequency of monitoring, and monitoring visits related to site closure after the end of the study.

9 Data Management

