1.4 Estimation of Sample Size

In a meta-analysis ^[1] comparing BGC with conventional guide catheter, the use of balloon guide catheter improved the proportion of functional outcome by 10.8%. In this study, based on a more conservative estimate, we assume the usage of BGC would improve the function outcome by 8%. Based on the distribution of the mRS in the control group of the trial, which we derived from the intervention group of the MR CLEAN trial : mRS0: 3%; mRS 1: 9%; mRS 2: 21%; mRS 3: 18%; mRS 4: 22%; mRS 5: 6% and mRS 6:21%. We assumed a favorable treatment effect with a common odds ratio (cOR) of 1.43, corresponding to an 8% absolute increase in the rate of mRS scores of 0-2. In a simulation with 5000 runs we computed the proportion of positive trials, for a given sample size. A sample size of 1074 subjects is estimated to be able to demonstrate this treatment effect with 87% power and 5% type-1 error. This sample size also allows for 5% dropout rate and 5% crossover rate.

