2.1.2.2 Secondary efficacy outcomes

- Dichotomized mRS of 0-1 vs. 2-6 at 90 days (\pm 14 days);
- Dichotomized mRS of 0-2 vs. 3-6 at 90 days (\pm 14 days);
- Dichotomized mRS of 0-3 vs. 4-6 at 90 days (\pm 14 days);

- Dichotomized mRS of 0-4 vs. 5-6 at 90 days (\pm 14 days);
- Dichotomized mRS of 0-5 vs. 6 at 90 days (\pm 14 days);
- Change in stroke severity (NIHSS score) at 24 hours post treatment;
- Change in stroke severity (NIHSS score) at 7 days post treatment or discharge, whichever occurs first;
- Final infarction volume (mL);
- Technical success rate;
- Reperfusion outcome(eTICI 2b or greater, eTICI 2c or greater, eTICI 3) in final angiogram;
- Reperfusion outcome(eTICI 2b or greater, eTICI 2c or greater, eTICI 3) after the first pass;
- Time from groin puncture to successful reperfusion(eTICI 2b or greater, eTICI 2c or greater);
- Percentage of subjects with acceptable revascularization quality (eTICI 2b or greater, eTICI 2c or greater) within 45 min of access;
- Number of thrombectomy attempts (final)
- Occurrence of emboli to a new territory

NIHSS Scale

The NIHSS is an ordinal hierarchical scale used to evaluate the severity of stroke by assessing the patient's physical strength. Scores may range from 0 to 42, with higher scores indicating more severe ischemia. Scale items includes level of consciousness, level of consciousness questions, loc commands, best gaze, visual, facial palsy, motor arm, motor leg, limb ataxia, sensory, best language, dysarthria, extinction and inattention (the criteria for scoring are detailed in Appendix 1).

NIHSS scores assessment will be collected at baseline, 24 ± 12 hours and 7 ± 2 days post treatment.

eTICI Scale

The eTICI classification includes 0, 1, 2a, 2b, 2c and 3 (eTICI criteria are detailed in Appendix 2).

eTICI grading will be collected before and after treatment.

Technical success rate

The technical success rate is defined as successfully navigating the guide catheter into the target vessel, and finishing the mechanical thrombectomy procedure without changing to another guide catheter.

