2.3.5.2 Secondary efficacy outcomes

For binary efficacy outcomes (dichotomized mRS at day 90, reperfusion outcome in final angiogram, reperfusion outcome after the first pass, occurrence of emboli to a new territory, technical success rate and percentage of subjects with acceptable revascularization quality), between-group comparisons will be performed by using a Chi-squared test or Fisher's exact test when applicable. The binary secondary efficacy outcomes also will be analyzed by logistic regression analysis to provide an odds ratio and its 95% CI, if applicable. The adjustment factors are the same as those in the primary outcome analysis.

For continuous efficacy outcomes (infarction volume, the change in NIHSS score at 24 hours post treatment from baseline and change in NIHSS score at 7 days post treatment or discharge from baseline), between-group comparisons will be done using a linear model adjusted for the prognostic factors considered in the primary outcome analysis, as appropriate; the adjusted mean difference will be derived from a linear model as treatment effect sizes. In case of obvious deviation from normality of the model residuals (except if a logarithmic transformation or other common transformation could be applied), a non-parametric analysis with the Mann-Whitney U test will be used and standardized differences will be calculated. Rank-transformed data will be provided as treatment effect size.

For count variable (number of thrombectomy attempts), it will be analyzed by using a negative binomial model ^[3] with the count data as dependent variable and treatment group as fixed-effect factors adjusted for the prognostic factors considered in the primary outcome analysis, as appropriate. The model estimated event rates and its 95%

confidence intervals will be provided by treatment groups. The treatment comparison will be performed through the estimated ratio of risk rates.

For time-to-event variable (time from groin puncture to successful reperfusion), it will be analyzed using the Cox's proportional hazards model with a fixed treatment group factor and adjusted for the prognostic factors considered in the primary outcome analysis, as appropriate. The estimated hazard ratio and the corresponding two-sided 95% CI will be provided. The Kaplan-Meier curves by treatment groups will be presented.

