2.3.5.3 Subgroup analyses

For the primary outcome, pre-specified subgroup analyses will be performed by examining the interaction between specific baseline characteristics and treatment. Subgroups are defined as follows:

- age (above vs. below median)
- onset time to randomization (<6 vs. \geq 6 h)
- NIHSS at baseline (above vs. below median)
- occlusion location (internal carotid artery vs. middle cerebral artery)
- presumed etiological AIS subtype (intracranial atherosclerosis vs. extracranial lesion vs. cardioembolism vs. other/undetermined)
- preferred treatment strategy (stent retriever vs. aspiration vs. stent retriever + aspiration)
- Tandem lesion (Yes vs. No)
- Intravenous thrombolysis (Yes vs. No)

The analysis for each subgroup will be performed by adding the subgroup variable as well as its interaction with the intervention as fixed effects to the main logistic regression model. Within each subgroup, summary measures will include raw counts and percentages by treatment arm, as well as the OR for treatment effect with a 95% CI. The output results will be displayed on a forest plot, including the p-values for heterogeneity corresponding to the interaction term between intervention and each subgroup variable.

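### If proportional odds is judged to fail, the primary test reads as switching to an unadjusted Mann-Whitney test with no stated trigger; the adjusted ordinal model should stay primary

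*SAP*

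**What the plan says.** SAP 2.3.5.1 states: "The primary efficacy outcome analysis will be conducted by using ordinal logistic regression analysis adjusted for prognostic factors, including center as a random effect". The fixed covariates are preferred strategy, onset-to-randomisation time, pre-stroke mRS, and age and baseline NIHSS, each split at the median. The section ends with the fallback: "In case of deviations in proportional odds assumption, the mRS score at day 90 will be compared between groups by using the Mann-Whitney U test", with a Wilcoxon-Mann-Whitney generalised odds ratio as the effect size. It does not say how proportional odds is to be checked, at what threshold, for which terms (treatment or any covariate) or by whom. It attaches no covariates or strata to the Mann-Whitney test.

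Protocol 7.2 says only: "The primary outcome will be analyzed by means of an ordinal logistic regression". It leaves the detail to the SAP and mentions no fallback.

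Three other places matter. SAP 1.4 sets the design effect on the common odds ratio scale: "We assumed a favorable treatment effect with a common odds ratio (cOR) of 1.43". SAP 2.3.5.3 builds each subgroup analysis by adding the subgroup variable and "its interaction with the intervention as fixed effects to the main logistic regression model". For continuous secondary outcomes with non-normal residuals, SAP 2.3.5.2 uses a parallel construction: "a non-parametric analysis with the Mann-Whitney U test will be used and standardized differences will be calculated".

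**The concern.** SAP 2.3.5.1 does not use the word 'instead', but replacement is the natural reading: a condition, then another test and another effect size, as in the parallel sentence of SAP 2.3.5.2. On that reading, a judgement about an assumption, made on the trial's own data, changes the primary test, removes the planned adjustment and moves the headline result off the common odds ratio. The overall result would then be on a different scale from the design effect and the subgroup forest plot. With no trigger, the choice between two tests that can disagree is left open. If the covariates are prognostic, as the SAP calls them, precision is given up as well.

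**Working it through.** **1. The plan's own figure.** Inputs: control mRS 0 to 6 of 3/9/21/18/22/6/21% and common odds ratio (cOR) 1.43 (SAP 1.4); N = 920, two-sided alpha 0.05, power 87% (Protocol Synopsis). Multiplying the control cumulative odds by 1.43 moves mRS 0-2 from 33.0% to 41.3% (+8.3 points). With p̄ the mean of the two arms' category probabilities, Σp̄³ = 0.0348. Whitehead's formula is

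power = Φ( ln(OR) × √[N/12 × (1 − Σp̄³)] − z )

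= Φ(0.3577 × √(76.67 × 0.9652) − 1.960) = Φ(3.077 − 1.960) = 86.8%, against 87% stated. At the final alpha of 0.0482 (SAP section 4; z = 1.9756) it is 86.5%.

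**2. What the switch amounts to.** In 5,000 simulated trials at that design (alpha 0.05), the *unadjusted* ordinal model had 86.94% power and Mann-Whitney 86.92%. Their z-statistics correlated at 0.99999 and the decisions differed in 0.02% of trials. Switching to Mann-Whitney is therefore close to deleting the covariates from the planned model.

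**3. Is the switch needed for validity?** With no treatment effect, the treatment odds ratio is 1 at every cut-point, so proportional odds holds for treatment. Simulated type I error at alpha 0.0482 was 4.7-4.9% for the adjusted model and 4.7-4.9% for Mann-Whitney.

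**4. Power.** Setup: 460 per arm, alpha 0.0482, planned control mRS, 20,000 trials per scenario. Age and NIHSS are independent 50/50 binaries, and the fitted model has treatment, age and NIHSS. Assumed conditional age/NIHSS odds ratios: none 1/1, weak 1.3/1.5, moderate 2/2, strong 2.5/3. Five non-proportional shapes were used; in the moderate case, for example, one has cut-point odds ratios falling from 2.14 to 1.00 and another has benefit overall but 0.91 at death. The illustrative trigger is a 5% score test of cut-specific treatment slopes, since the SAP names none. The paired standard error of a difference is at most 0.26 points.

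Adjusted minus Mann-Whitney power, in percentage points:

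| Scenario | None | Weak | Moderate | Strong |
|---|---|---|---|---|
| Non-proportional, average cOR 1.43 | 0.0 to 0.2 | 0.5 to 0.8 | 1.7 to 3.0 | 3.5 to 5.4 |
| Non-proportional, 8-point gain in mRS 0-2 | -0.1 to 0.3 | 0.2 to 1.1 | 0.7 to 3.5 | 0.9 to 7.5 |
| Only trials where the trigger fired (both calibrations) | 0.0 to 0.4 | 0.2 to 1.2 | 0.7 to 3.7 | 0.9 to 7.2 |
| Averaged over all trials, with the trigger | 0.0 to 0.2 | 0.2 to 0.7 | 0.6 to 2.3 | 0.7 to 4.6 |

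In the second row, the smallest weak, moderate and strong figures come from a shape whose power is already 98-99%. Over all 48 scenarios (4 strengths × 6 shapes, including the proportional one, × 2 calibrations), Mann-Whitney was never ahead by more than 0.1 point.

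**5. If proportional odds holds (cOR 1.43).** Adjusted power is 86.5/87.4/89.1/91.4% against 86.6/86.8/86.2/86.3% for Mann-Whitney. The trigger fires in about 5% of trials, so the average loss is only 0.0/0.0/0.1/0.3 points.

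**6. If only a covariate is non-proportional.** In the moderate case, with the NIHSS odds ratio running from 1.5 to 2.7 across cut-points, a joint 5% check of all terms fires in 21% of trials. The adjusted test keeps its size (4.8-5.0%) and is 2.8-3.0 points more powerful.

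**7. The open choice.** A fixed 5% trigger keeps type I error at 4.7-4.9%. Always taking the smaller p-value, which the SAP does not prescribe, would give 5.0/5.4/6.2/6.6%.

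**8. Other assumptions.** A separate simulation gave age and NIHSS equal odds ratios and added weak effects of pre-stroke mRS and onset time (4,000 trials per scenario, alpha 0.05). The adjusted model led by 1.1, 2.9 and 6.1 points under proportional odds (odds ratios 1.5, 2 and 3), and by 3.5-6.3 (odds ratio 2) and 7.3-12.7 points (odds ratio 3) under four other non-proportional shapes. With odds ratio 1 the tests tied. The direction is the same, but the sizes move with the assumptions.

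**The case against.** The strongest case against is that nothing invalid has been shown. Both tests and a fixed trigger hold their size, the fallback is pre-specified, and the planned 87% survives a switch when proportional odds holds. The sample-size text never counts on a gain from adjustment. Under the plan's own common-odds-ratio assumption the average loss is at most 0.3 points. Larger losses need assumed covariate strengths and assumed shapes, and the top of the range also treats the switch as certain. The simulations did not fit the full planned model: the centre random effect was left out throughout. All of that stands, and it limits how far any single figure can be relied on.

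It can also be said that the SAP promises adjusted and unadjusted common odds ratios without condition, so Mann-Whitney might be meant as an addition. That reading is possible. If it is the intended one, the proposed sentence simply states it.

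Finally, the generalised odds ratio is an effect measure that does not need proportional odds, whereas the common odds ratio becomes an average over cut-points when the assumption fails. That is true, but the generalised odds ratio is also one summary over the scale, and it remains available as a sensitivity analysis. Naming a trigger would close the open choice but would not restore the adjustment or the planned effect measure.

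**Conclusion.** The concern holds. The fallback protects no error rate and gains no power. If the covariates are prognostic, it gives up some of what the primary model was specified to deliver. Under non-proportional treatment effects with average cOR 1.43, the cost of switching runs from about zero (non-prognostic covariates) to 3.5-5.4 points (strong ones). Averaged over trials with an illustrative 5% trigger, and over both calibrations, it is 0.0 to 4.6 points. These sizes rest on assumed covariate strengths and shapes and on a model with age and NIHSS only; the direction did not depend on them. The loss is relative to the adjusted model, not to the planned 87%. Whatever the strengths, the missing trigger and the change of effect measure remain.

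**What to change.** Replace the last sentence of SAP 2.3.5.1 with:

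> The covariate-adjusted ordinal logistic model gives the primary p-value and common odds ratio whatever the check of proportional odds shows. The Mann-Whitney U test and the Wilcoxon-Mann-Whitney generalised odds ratio will be reported as a pre-specified sensitivity analysis, beside the five dichotomised mRS comparisons.

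Those comparisons are already planned in SAP 2.1.2.2 (for example "Dichotomized mRS of 0-2 vs. 3-6 at 90 days") and will show the shape of any departure from proportional odds. The cost is SAP wording only, before database lock. The one downside is that, under marked non-proportionality, the headline common odds ratio must be read as an average over cut-points.
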